5.3.6 CYP3A4 Inhibitors: Dose modifications

Venetoclax

-Venetoclax should be administered at 50% dose reduction in the setting of moderate CYP3A inhibitor and at 75% dose reduction in the setting of strong CYP3A inhibitor for the duration of co-administration. The dose will be reduced by 75% if patient is on posaconazole.

-In the event the co-administered CYP3A inhibitor is discontinued, the assigned venetoclax dose should be resumed 2-3 days after discontinuation.

-Every effort should be made to adhere venetoclax dose reduction. Variations in schedule of events such as late/missed interventions that do not affect the rights and safety of the patient will not be considered as deviations.

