Clinical Efficacy Data for Venetoclax: Preliminary efficacy results are available for subjects with a variety of hematological neoplasms; the drug is approved for the treatment of CLL patients whose cells have a 17p chromosomal deletion. Preliminary data indicate that venetoclax shows promising efficacy in AML.

- In Study M14-212 the CR/CRi rate for subjects treated with venetoclax monotherapy was 19% (Konopleva M et al, *Cancer discovery* 2016; **6**(10): 1106-17).
- In Study M14-358 the CR/CRi rate for AML subjects (given venetoclax plus azacitidine or decitabine) was 66% (DiNardo CD et al, *Blood*. 2019 Jan 3;133(1):7-17).
- In Study M14-387 the CR/CRi rate for AML subjects (given venetoclax plus low dose ara-C) was 54% (Wei A et al [J Clin Oncol.](#) 2019 May

Venetoclax Clinical Pharmacology and Pharmacokinetics: Venetoclax clinical pharmacology is being evaluated in several Phase I to III clinical trials, and data are available from three Phase I studies (M12-175, M13-367, M12-630), four Phase Ib studies (M13-365, M12-901, GO29440, GP28331), one Phase II study (M14-212) and five dedicated clinical pharmacology studies (Study M13-364, M14-497, M13-363, M14-253 and M15-101).

In the Phase 1 Study M14-358, preliminary pharmacokinetic results in 31 treatment-naïve AML subjects were available for venetoclax doses ranging from 400 mg to 800 mg when given in combination with decitabine (Arm A) or azacitidine (Arm B) and with or without posaconazole (Arm C). For Arm A and Arm B, venetoclax steady-state mean Cmax and AUC24 (Cycle 2 Day 5) ranged from 1.77 – 3.36 µg/mL and 24.7 – 59.5 µg/mL, respectively. Based on the limited preliminary pharmacokinetic data, there was no evidence to suggest a marked effect of the co-administration of decitabine and azacitidine on the pharmacokinetics of venetoclax. In Arm C of this study, preliminary pharmacokinetic results from 6 subjects were available on Cycle 1 Day 20 (venetoclax 400 mg alone QD until Day 20) and Cycle 1 Day 28 (venetoclax 100 mg QD with posaconazole given from Day 21 to Day 28). Venetoclax Cmax and AUC following co-administration of venetoclax 100 mg with posaconazole were 2.1- and 2.7-fold higher respectively, compared to venetoclax 400 mg alone.

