Table 5C: Arm 3: Dose levels of 5-azacytidine, nivolumab and venetoclax during the lead-in phase (part a)

| Dose level | 5-azacytidine (mg/m ² /d, Days 1-7) | Nivolumab (mg/kg, day 8 and 22) | Venetoclax (400mg or equivalent) |
|---|---|------------------------------------|-------------------------------------|
| -2 | 75 | 1.0 | D1-14 |
| -1 | 75 | 1.0 | D1-21 |
| 0 (starting dose and target dose)) | 75 | 3.0 (starting dose) | D1-21 |

The goal of the lead-in phase is to identify the MTD i.e. the dose at which <2/6 patients experience DLT. During the lead-in phase the dose/s/duration of nivolumab and/or venetoclax may be reduced if 2 or more patients experience DLT at any given dose as shown in Table 5C. The RP2D will be selected at the end of the lead-in phase and may be the MTD dose or a dose level lower than the MTD.

Once the RP2D is decided the expansion (part b) will open in 2 cohorts: Frontline cohort (n=30) and Salvage Cohort (n=30) with eligibility as defined in 4.2.1. See “statistics” section for more details.

After the lead-in (part a) the dose of nivolumab may NOT be reduced in the expansion (part b) of the study. For potential nivolumab related AEs only dose interruptions will be permitted. Dose reductions or escalations of venetoclax and 5-azacytidine are permitted in the expansion (part b) of the study and dose reductions or escalations of 5-azacytidine or venetoclax beyond those mentioned in table 5C or 5.3.2 should be discussed with the PI and documentation of the justification recorded in the chart. Only Salvage patients as defined in Inclusion criteria 4.1B will be enrolled during in the lead-in phase.

The dose and /or schedule of administration is subject to modification pending information from ongoing clinical trials of nivolumab or ipilimumab or venetoclax as a single agent and in combination with other drugs.

DLT is defined as clinically significant non-hematologic adverse event or abnormal laboratory value assessed as unrelated to disease progression, intercurrent illness, or concomitant medications and occurring during the first cycle on study that meets any of the following criteria:

- CTCAE Grade 3 AST (SGOT) or ALT (SGPT) for ≥= 7 days or grade 3 hyperbilirubinemia for ≥= 7 days
- CTCAE Grade 4 AST (SGOT) or ALT (SGPT) of any duration
- All other clinically significant non-hematological adverse event that is Grade 3 or 4 according to the NCI common terminology criteria version 4.0 with the following exceptions:

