- During cycle 1, venetoclax will be dose escalated daily to the goal dose of 400mg daily. Patients will receive 100mg on Day 1, 200mg on Day 2 and 400mg on Day 3 and onwards, or adjusted dose if on concomitant azoles (discussed below in section 6.3). Venetoclax dose ramp-up as described in section 6.4.
- If venetoclax is not available at the start of therapy due to different reasons (insurance, financial, transportation, others), azacitidine and nivolumab can start and venetoclax is added when it becomes available.
- If azacitidine cycles are delayed, venetoclax therapy may continue on Days 1-21 of a 4-week cycle after discussion with the PI or Co-PI and documentation in the medical record. If azacitidine cycles are delayed, nivolumab may continue as scheduled (q2 weeks) after discussion with the PI or Co-PI and documentation in the medical record.

5.2.2 One cycle of therapy is defined as 28 days. Patients will receive one cycle of therapy every 28 days (+/- 7 days). The ipilimumab will be given every 6 weeks (+/-3 days).

5.2.2.1 In the expansion (part b) portion of the study (once the MTD/RP2D dose has been defined) cycles may be started early (but not earlier than day 21) for patients with active disease if judged in the best interest of the patient.

Nivolumab and azacytidine

For the lead-in (part a) cohort, DLT defining period is 28 days. As such, cycle 2 should not be started before 28 days for the patients being treated on the lead-in cohort.

5.2.2.2 Subsequent cycles may be delayed for recovery of toxicity or other medical conditions (e.g. infections). Delays in start of subsequent cycles greater than 8 weeks will be acceptable only for patients who are deriving clinical benefit and after discussion with the principal investigator of potential risk/benefit ratio.

5.2.2.3 In instances where one drug has to be discontinued transiently because of safety, the administration of the other drug may continue as scheduled. If the drug that is held can resume at a later time, no doses will be made up and the administration will follow the originally defined schedule calendar according to the drug that was continued.

5.2.2.4 Subsequent courses of 5-azacytidine and nivolumab OR 5-azacytidine with nivolumab and ipilimumab OR 5-azacytidine with nivolumab and venetoclax may be administered regardless of peripheral blood counts during the first 4 cycles and/or in the presence of residual leukemia.

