Concomitant medications are recommended as prophylaxis for nausea, vomiting, and infections, and are allowed for managing myelosuppression as shown in Table 8. Myelosuppression is expected in patients with AML due to underlying disease, as well as due to chemotherapy (such as 5-azacytidine and venetoclax), or both. Most patients have neutropenia, thrombocytopenia, or both at study entry. Significant or life-threatening myelosuppression may be managed with growth factor support and blood transfusion according to institutional standard of care, American Society of Clinical Oncology (ASCO) Practice Guidelines, and/or NCCN Practice Guidelines.

Infections secondary to myelosuppression are common in patients with AML, and may be related to underlying disease, chemotherapy, or both. Therefore, the use of prophylactic antibiotics, antifungal agents, and antiviral agents is recommended according to institutional standards.

Since the effect of both nivolumab and 5-azacytidine may be delayed, patients with high WBC counts may receive hydroxyurea and up to 1 dose of cytarabine (up to 2 g/m²) prior to study entry. Hydroxyurea is allowed before the start of study therapy and during the study treatment. Hydrea and cytarabine use would be recorded in the CRF. Concurrent therapy for CNS prophylaxis or continuation of therapy for controlled CNS disease is permitted. With the exception of these agents, concomitant systemic chemotherapy or concurrent radiation therapy for other (non AML) cancers should be discussed with the PI and may be approved by the PI on a case-by-case basis. Subjects are not allowed to participate concurrently in any other therapeutic clinical study.

Subjects may be receiving systemic corticosteroids (daily doses \leq 10 mg of prednisone or equivalent if indicated for adrenal replacement or antiemetic therapy), topical, or inhaled corticosteroids at study enrollment. They may receive systemic, topical, inhaled, or enteric corticosteroids while on study without limitation if they develop conditions that require corticosteroid therapy; such subjects are not required to discontinue study participation.

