All ongoing medications and therapies (including herbal products, nutritional supplements, and nontraditional medications) at screening will be considered prior medications. Concomitant medication data will not be collected or entered into the case report form other than hydrea and cytarabine as mentioned above; however, the subject's medication record will contain a list of concomitant medications. If a prohibited medication is inadvertently administered/ taken by the patient, the patient may remain on study as long as the prohibited medication is discontinued as soon as feasible. If a prohibited

Nivolumab and azacytidine medication is considered essential for the patient well being, continuation on study with concomitant administration of such medication(s) will need to be discussed with and approved by the principal investigator and medical monitor.

Investigational agents that are not used for treatment of the leukemia per se (e.g. anti-infective prophylaxis or therapy) will be allowed. Other supportive care studies are allowed, even if under an IND.

Table 8: Instructions for the use of concomitant medications and therapies

| Category of Use | Medication | Comment on Use | Restriction on Use |
|-----------------|--|---|---|
| Recommended | Prophylactic antibiotics, antifungal agents, and antiviral agents | Strongly encouraged | None |
| | Antiemetic agents | According to standard of care at MDACC | None |
| Allowed | Oral allopurinol or rasburicase Leukapheresis Red blood cell transfusion | At investigators discretion According to standard of care at MDACC None | None Before induction 1 day 1 only None |
| | Platelet transfusion | None | None |
| | White blood cell transfusion | At investigators discretion according to standard of care at MDACC | None |
| | Myeloid growth factors or platelet growth factor | At investigators discretion according to standard of care at MDACC | None |
| | Erythropoietin or darbepoetin | At investigators discretion | None |
| | Any other medication for supportive care | At investigators discretion according to standard of care at MDACC | None |

MDACC = MD Anderson Cancer Center

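### By the protocol's only PK figure, the Arm 3 venetoclax adjustment for posaconazole is not exposure-equivalent to 400 mg, so the lead-in MTD may be confounded by inhibitor use that no planned summary shows

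*Combined protocol and SAP*

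**What the plan says.** Without an interacting drug, Arm 3 venetoclax is ramped to its target in cycle 1: "Patients will receive 100mg on Day 1, 200mg on Day 2 and 400mg on Day 3 and onwards" (Arm 3 instructions following section 5.2.1.7). The same sentence allows for a different dose with azoles and sends the reader to section 6.3. Section 5.3.7 repeats both the ramp-up and the pointer. Section 6.3 is about ipilimumab.

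The rule itself is in section 5.3.6: a 50% cut with a moderate CYP3A inhibitor, a 75% cut with a strong one and, for one named drug, "The dose will be reduced by 75% if patient is on posaconazole".

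Table 5C heads its venetoclax column "Venetoclax (400mg or equivalent", and this covers all three Arm 3 lead-in levels. The meaning of *equivalent* is not given.

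Section 2.6, describing Arm C of study M14-358, reports: "Venetoclax Cmax and AUC following co-administration of venetoclax 100 mg with posaconazole were 2.1- and 2.7-fold higher respectively, compared to venetoclax 400 mg alone". It presents these as preliminary results from 6 subjects, measured on Day 20 (400 mg alone) and Day 28 (100 mg with posaconazole).

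A level qualifies as the MTD if fewer than 2 of 6 patients have a DLT in the first 28 days (sections 5.2.1.7 and 11.3). The lead-in rules neither restrict CYP3A inhibitors nor separate patients by their use. Evaluability (section 5.2.2.6) counts venetoclax doses taken, 18 of 21, and not their size.

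On antifungals, section 5.6 states that "the use of prophylactic antibiotics, antifungal agents, and antiviral agents is recommended according to institutional standards", and Table 8 encourages this strongly and without restriction. On recording, the same section states: "Concomitant medication data will not be collected or entered into the case report form other than hydrea and cytarabine". Other drugs stay in the patient's medication record (sections 5.6 and 7.3.7).

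**The concern.** The protocol uses one label for doses that its own data show to be unequal in exposure. The dose after the section 5.3.6 cut is exactly the dose tested in section 2.6, so no extrapolation is needed to see the conflict, and no reason is given for it.

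The lead-in is where this matters for inference. The MTD rests on 6 patients and a threshold of 2 events. If some of the 6 take posaconazole and others do not, they count as one dose level while their exposure may differ more than twofold. A level could then fail because of its users, or pass because it happened to have few of them and not represent the expansion cohorts. Those who make the decision would not be shown which patients were which, since neither the CRF nor the cohort summary is required to carry inhibitor use.

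**Working it through.** **Inputs.** Target dose 400 mg (ramp-up instructions and section 5.3.7). Reduction 75% (section 5.3.6). Exposure with 100 mg plus posaconazole relative to 400 mg alone: Cmax 2.1, AUC 2.7 (section 2.6). These are read as ratios, the smaller of the two possible readings. They are reported observations and cannot be recomputed, because the Arm C concentrations are not given. MTD rule: 0 or 1 DLT in 6. The planned lead-in size reproduces: 3 levels × 6 = 18 (section 11.2).

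**Step 1: the adjusted dose.** 400 × (1 − 0.75) = 100 mg, the dose in the section 2.6 comparison.

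**Step 2: what the cut offsets.** Going from 400 to 100 mg restores the original exposure only if posaconazole raises exposure per mg by 400/100 = 4-fold. The reported ratios imply 2.7 × 4 = 10.8-fold for AUC and 2.1 × 4 = 8.4-fold for Cmax.

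**Step 3: compared with the steps in Table 5C.** Venetoclax varies between levels only in duration: 21 against 14 days, or 21/14 = 1.5-fold in cumulative dose. A 2.7-fold AUC difference inside a level is larger than that step.

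**Step 4: effect on the MTD rule.** The documents give no DLT rate by posaconazole use, so these rates are assumptions. With k users among 6, DLT rate p0 off and p1 on posaconazole, and independent patients:

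P(level passes) = P(X + Y ≤ 1), with X ~ Bin(6 − k, p0) and Y ~ Bin(k, p1).

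Worked case, k = 3, p0 = 0.10, p1 = 0.30:

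- P(no DLT) = 0.9³ × 0.7³ = 0.729 × 0.343 = 0.250
- P(one DLT) = 3 × 0.1 × 0.9² × 0.343 + 0.729 × 3 × 0.3 × 0.7² = 0.083 + 0.321 = 0.405 (from unrounded terms)
- P(pass) = 0.655

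| p0 / p1 (assumed) | k = 0 | k = 1 | k = 2 | k = 3 | k = 6 |
|---|---|---|---|---|---|
| 10% / 20% | 0.886 | 0.853 | 0.816 | 0.778 | 0.655 |
| 10% / 30% | 0.886 | 0.820 | 0.740 | 0.655 | 0.420 |
| 10% / 40% | 0.886 | 0.787 | 0.656 | 0.525 | 0.233 |
| 15% / 15% | 0.776 | 0.776 | 0.776 | 0.776 | 0.776 |

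**Step 5: how likely is a mixed cohort?** With a share f of patients on posaconazole, the chance that all 6 have the same status is f⁶ + (1 − f)⁶. For assumed f of 20%, 50% and 80% this is 0.26, 0.03 and 0.26. Within that range, most cohorts would be mixed.

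**The case against.** The PK evidence is thin: "preliminary pharmacokinetic results from 6 subjects were available on Cycle 1 Day 20", with no interval, and for posaconazole alone. Nothing is reported for other strong or moderate inhibitors. The venetoclax label is cited but not reproduced, so the basis of the 75% rule cannot be checked here. This limits confidence in the 2.7, but it remains the only figure the protocol offers.

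A reader might infer that posaconazole is recommended and its users will be common. The recommendation covers antifungals as a class and names no agent. The protocol plans for azoles and names posaconazole in section 5.3.6, but the share exposed is unknown.

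A reader might also convert the AUC ratio into 2.7 × 400 = 1,080 mg of venetoclax. That assumes dose proportionality. Even on that assumption, section 2.6 reports venetoclax with a hypomethylating agent at 400, 800 and 1200 mg with no MTD reached. This weakens the link from exposure to DLTs without removing it: follow-up at 1200 mg was shorter, the patients were treatment-naive, and nivolumab was not given.

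It would be too strong to say that the data cannot show inhibitor use. Concomitant drugs are documented at the start of each cycle (section 7.3.1) and listed in the medication record, and the lead-in has at most 18 patients, so retrieval is feasible. What stands is that no planned summary asks for it.

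There are partial safeguards. A non-hematologic DLT must be judged unrelated to concomitant medication, but that does not say how to classify venetoclax toxicity raised by an interaction, and the hematologic definition has no such clause. The RP2D may be set below the MTD. Expansion cohorts are monitored every 5 patients, but section 5.2.2.6 describes this as covering non-hematological grade 3/4 events.

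**Conclusion.** The contradiction stands. Section 5.3.6 and Table 5C treat 100 mg with posaconazole as matching 400 mg, while section 2.6 reports 2.1 times the Cmax and 2.7 times the AUC. The two cross-references to section 6.3 are also wrong.

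The consequence for the MTD is a risk of unknown size. A reader might conclude that the Arm 3 MTD is confounded; the documents support only that it may be. Confounding needs cohorts that mix users and non-users, or that differ in mix from the expansion, and it needs extra exposure to raise the DLT rate. The documents give neither the mix nor the rates. The fall in pass probability from 0.886 to 0.655 with three users is an illustration under assumed rates of 10% and 30%; with equal rates there is no change. This should be fixed, and confidence is moderate. Nothing here bears on which venetoclax dose is right.

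**What to change.** - Reconcile section 2.6, Table 5C and section 5.3.6, and state what *equivalent* means and on what basis. This review proposes no dose.
- For Arm 3, record in the CRF the name of any CYP3A inhibitor, its start and stop dates, and the venetoclax dose actually given.
- In the cohort summary that sections 5.2 and 11.3 already require before dose-level decisions, list each patient's inhibitor status beside DLT status. A plain listing is enough; formal stratification of 6 patients would add little.
- Describe expansion toxicity by inhibitor use.
- In the ramp-up instructions after section 5.2.1.7 and in section 5.3.7, change the azole pointer from section 6.3 to section 5.3.6.

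The cost is a short amendment, a few CRF fields largely available from the medication record, and a column in an existing summary. The downside is slightly more data entry in Arm 3.

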5.3.7 Tumor Lysis Prophylaxis (TLS)

-The venetoclax dose titration scheme utilized in the AML studies performed to date to mitigate the risk of tumor lysis syndrome (TLS) will be employed. All patients will be hospitalized for the entirety of the venetoclax dose escalation starting at least on day 1 of treatment initiation and until 24 hours after the completion of venetoclax dose escalation. During cycle 1, venetoclax will be dose escalated daily to the goal dose of 400mg daily. Patients will receive 100mg on Day 1, 200mg on Day 2 and 400mg on Day 3 and onwards, or adjusted dose if on concomitant azoles (discussed below in section 6.3).

-To mitigate the risk for TLS, subjects must be receiving tumor lysis prophylaxis, including hydration (oral, intravenous) and treatment with a uric acid reducing agent (allopurinol, rasburicase) prior to start of venetoclax and at least during the first cycle of therapy.

-TLS chemistry tests (potassium, uric acid, creatinine, calcium and phosphorus) will be obtained prior to dosing and 5-8 hours after each day of a new venetoclax dose. TLS chemistry test results will be reviewed by the investigator in real time and prior to the subject's next dose to ensure appropriate management. If a subject meets criteria for clinically significant laboratory or clinical TLS, no additional venetoclax should be administered until resolution.

Nivolumab and azacytidine

-Venetoclax interruption for up to 72 hours following transient (< 48 hours) chemical changes and laboratory TLS will be allowed and will not require a dose reduction.

5.3.8 Meals and Dietary Requirements:

-Each dose of venetoclax should be taken with approximately 240 mL of water within 30 minutes after the completion of a meal, preferably breakfast.

-Subjects should not consume grapefruit or grapefruit products, Seville oranges, or Star fruit within the 3-day period prior to the first venetoclax administration and until the last day of venetoclax is completed due to possible CYP3A mediated metabolic interaction.

5.3.9 Intra-patient dose re-escalation for patients who have had dose-reductions due to hematological or non-hematological toxicity:

Once the MTD has been established in the lead-in, the nivolumab dose (Arm 1 or 3) or nivolumab+ipilimumab dose (Arm 2) will not be reduced or escalated during the phase II portion. Intra-patient dose re-escalation of 5-azacytidine and/or venetoclax will be permitted provided:

- Patient has completed $>/=1$ cycle at their current dose level
- Patient has not experienced any grade 3 or higher non-hematologic drug-related toxicity, and
- Patient has not experienced drug-related hematologic DLT, and
- At least 6 patients have been treated at the next higher dose level and followed for at least 28 days without experiencing DLT.
- The dose may be escalated by one dose level per cycle (per section 5.3.2) provided such dose level does not exceed the established MTD or dose level 0, whichever is lower. Dose level 0 (Table 5A, 5B, 5C) is the maximum dose allowed on this study. No dose escalation beyond dose level 0 will be permitted.

5.3.10 Modifications of dose schedules other than the above will be allowed within the following guidelines:

5.3.7.1 Further dose reductions can be made to keep clinically significant toxicities grade ≤ 2 .

5.3.7.2 Dose adjustments by more than 1 dose level at a time (e.g., from 5-azacytidine 75 mg/m² to 25 mg/m²) can be considered when judged in the best interest of the patient (e.g. severe myelosuppression) when toxicity has resolved. The reason for this reduction must be discussed and approved by the PI or Co-

PI and documented in the medical record.

5.3.7.3 A patient who has had a dose reduction because of any of the reasons mentioned above may have their dose escalated provided the patient has remained free of toxicity requiring dose adjustments as defined above for at least 1 month. Escalation will be made by 1 dose-level increment only, and not more frequent than every month.

5.3.7.4 Treatment interruptions and dose modifications other than the ones mentioned above can be considered after discussion and approval by the PI or Co-PI and proper documentation of the rationale.. Dose adjustment/delay of only one of the agents is permissible if the toxicity is most likely judged to be related to one of the agents by the investigator (e.g., in patients with autoimmune thyroiditis or autoimmune hepatitis this would be likely secondary to nivolumab or nivolumab+ipilimumab, in patients with cytopenia's this would be likely secondary to 5-azacytidine or venetoclax).

